1.4 Vigil Clinical Experience

Since the initiation of clinical trials with Vigil in 2009, over 160 patients have received treatment with the therapy and over 900 doses have been administered in completed and ongoing studies. The most frequently reported adverse reactions attributed to Vigil engineered cell administration are injection site reactions which are mild to moderate in intensity, consisting primarily of redness and swelling at the injection site. These occur in essentially all Vigil treated patients. To date, there have been no severe or life threatening (CTC Grade 3 or 4) adverse events attributed to Vigil treatment.

An early report (Senzer et. al. 2012) summarized the initial experience in 27 patients treated with the Vigil cellular immunotherapy construct (named FANG at the time), and in a matched control group of 18 patients. All patients underwent surgery for procurement of tumor tissue and manufacture of Vigil, however, the matched control group of 18 patients did not receive Vigil due to patient choice (14), failure to satisfy eligibility criteria (2) or failure of manufacture (2). Patient characteristics and dosing information are summarized in Table 1 below.

Characteristic	No Vigil	Vigil	All		
	(n = 18)	(n = 27)	(n = 45)		
Age (years)					
Mean	56	59	57		
Median	56	62	57		
Range	39–73	26–84	26-84		
Gender					
Male	9	8	17		
Female	9	19	28		
Dose level					
1.0 × 10e7 cells/ml	8	10	18		
2.5 × 10e7 cells/ml	8	17	25		
Vaccine failure	2	N/A	2		

Table 1. Patient Characteristics

Both GMCSF transgene expression and downregulation of expression of TGF β 1 and TGF β 2 were apparent in all successfully manufactured Vigil preparations. Mean post-transfection GMCSF expression increased from 7.3 to 1,108 pg/10⁶ cells/ml. Mean TGF β 1 and β 2 knockdown were 93.5% and 92.5%, respectively.

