Eligible patients were initially randomized 2 (Vigil): 1 (SOC). Patients received 1.0×10^7 cells / intradermal injection of Vigil once per month for up to 12 doses as long as sufficient material was available. Tumor procurement needed to be sufficient to supply a minimum of 4 monthly injections in order for a patient to be entered into the study. Treatment was continued until disease recurrence or exhaustion of the patient's vaccine supply. Clinical adverse events, as reported by the patient, were assessed continuously. Other scheduled safety assessments included monthly physical examination, performance status, height, weight, vital signs and laboratory evaluations. The primary efficacy endpoint was recurrence free survival assessed radiographically by the investigators. CA-125 was monitored at baseline, monthly for the first year, every 3 months \pm 2 weeks for the second and third year.

Serial immune function analysis including ELISPOT analysis of mononuclear cell function to pre-processed autologous tumor cells was monitored at baseline (screening), prior to Vigil injection and at Months 2, 4, 6 and at end of treatment (EOT). A positive response was defined as > 10 ELISPOTs induced per 10⁶ peripheral blood mononuclear cells (PBMC) and twice baseline response.

Results are reported in a total of 42 patients, 31 in the Vigil arm and 11 in the control arm. The original randomized design was abandoned after 21 patients were randomized into the Vigil arm of the study and 11 to the control arm, when the sponsor decided to initiate a definitive Phase 3 study. At that time, an additional 10 patients who were completing chemotherapy were allowed to receive Vigil without randomization.

A total of 241 intradermal (ID) injections of Vigil were administered to the 31 patients. The most frequent treatment emergent adverse events, considered related to therapy were injection site reactions of CTCAE Grade 1 or 2, which occurred in essentially all Vigil treated patients. There were no CTCAE Grade 3 or 4 treatment related adverse events amongst the Vigil treated patients.

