- 9. Patients with irreversible toxicity that is not reasonably expected to be exacerbated by the IPs (Vigil and/or atezolizumab) may be included (e.g., hearing loss) after consultation with the Principal Investigator
- 10. Subjects who are not rendered surgically sterile as a result of surgery for ovarian cancer, must have, negative urine or serum pregnancy test. If the urine test is positive or cannot be confirmed as negative, a negative serum test will be required for study entry.
- 11. Ability to understand and the willingness to sign a written informed protocol specific consent.
- 12. Willing and able to comply with the protocol for the duration of the study including undergoing treatment and scheduled visits and examinations including follow up.
- 13. Patients must have fully recovered from chemotherapy associated toxicities prior to starting treatment on this protocol.

Palliative radiotherapy is permitted provided:

- a. More than 3 weeks have elapsed between the end of radiotherapy and the first dose of study therapy, AND
- b. The irradiated lesion(s) (unless measurable progression after irradiation) cannot be used as target lesions.

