- Treatment delay not related to toxic events (including subjects unable to adhere to dose schedule) may not extend for more than three days unless due to symptoms related to disease or infection in which case up to a 4-week delay is allowed.
- If ≥ one 2-week delay due to disease or infection occurs, subject status must be reviewed by sponsor.

Atezolizumab should be permanently discontinued for any of the following AEs:

- Any life-threatening or Grade 4 AE
- Grade 3 or 4 pneumonitis
- Aspartate aminotransferase (AST) or alanine aminotransferase (ALT) >5 times upper limit of normal or total bilirubin >3 times upper limit of normal
- Diarrhea with abdominal pain, fever, ileus, or peritoneal signs; increase in stool frequency (Grade 4) stool incontinence, need for intravenous hydration for more than 24 hours, gastrointestinal hemorrhage, and gastrointestinal perforation
- Grade 4 hypophysitis
- Myasthenic syndrome/myasthenia gravis, Guillain-Barré or meningoencephalitis (all grades)
- Grade 3 or 4 ocular inflammatory toxicity
- Grade 4 or any grade of recurrent pancreatitis
- Grade 3 or 4 infusion-related reactions
- Grade 4 rash
- Grade 3 or 4 nephritis
- Myocarditis (all grades)

For combination treatment, the occurrence of a Grade 3 or 4 toxicity attributed to Vigil will result in the cessation of Vigil dosing and continuation of single agent atezolizumab only.

Please reference https://www.gene.com/download/pdf/tecentrig_prescribing.pdf for full prescribing information regarding atezolizumab.

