14.1 Attribution of Causality

The relationship of each event will be assessed by the Treating Physician and recorded on the CRF.

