14.5 Recording of an Adverse Event

Adverse events will be recorded for the duration of a subject's study treatment (following the first dose of Investigational Product, Vigil and/or atezolizumab), and for up to 30 days following the last study treatment or until another therapy has been initiated, whichever is earlier, regardless of causality.

SAEs and AESIs should be recorded for the duration of the study treatment and for up to 30 days following the last study treatment or the initiation of new therapy, whichever is earlier.

All AEs, regardless of causal relationship are to be recorded in the eCRF and source documentation. Additional information about each event, such as treatment required, eventual outcome, and whether or not therapy had to be interrupted or dosages reduced, will be noted in source documents and recorded on the eCRF.

Pre-existing conditions will be recorded at baseline on the Medical History Form. If a preexisting condition does not change, it does not have to be reported as an AE on subsequent cycles.

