16.0 STATISTICAL CONSIDERATIONS

16.1 Safety Analysis

The safety evaluation will include AEs, AESIs, SAEs, and changes from baseline in laboratory evaluations, vital signs, electrocardiograms, and physical examinations. The number and percentage of subjects reporting treatment emergent AEs will be summarized overall and by the highest Common Terminology Criteria for Adverse Events (CTCAE) grade, system organ class, and preferred term, with a breakdown by dose and tumor type. Similarly, the number and percentage of subjects reporting treatment-emergent AEs considered related to investigational product will be summarized. At each level of subject summarization, a subject will be counted once using the highest grade and level of causality if one or more occurrences of the same system organ class/preferred term is reported. Adverse events will be graded according to the National Cancer Institute (NCI) CTCAE v4.03 and coded using the Medical Dictionary for Regulatory Activities. Laboratory abnormalities will be graded according to the NCI CTCAE v4.03, if applicable.

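### Related adverse events are summarised against one pooled investigational product although two agents are given, so the any-grade related row will say almost nothing about atezolizumab

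*Combined protocol and SAP*

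**What the plan says.** Section 16.1 summarises treatment-emergent AEs overall and by highest CTCAE grade, system organ class and preferred term, broken down by dose and tumor type. For relatedness it adds that "subjects reporting treatment-emergent AEs considered related to investigational product will be summarized". At each level a subject counts once, at the highest grade and causality. No breakdown by agent or by treatment period is named.

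The term covers both agents. Section 14.5 starts AE recording "following the first dose of Investigational Product, Vigil and/or atezolizumab", and Section 5.4 allows irreversible toxicity that is "not reasonably expected to be exacerbated by the IPs (Vigil and/or atezolizumab").

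On causality, Section 14.1 says only: "The relationship of each event will be assessed by the Treating Physician and recorded on the CRF". It does not say whether that means one relationship per event or one per agent.

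The conduct rules do distinguish the agents. Under Section 6.2.2, in combination treatment, "the occurrence of a Grade 3 or 4 toxicity attributed to Vigil will result in the cessation of Vigil dosing", while atezolizumab continues. One of the withdrawal criteria in Section 5.6 also names Vigil, atezolizumab and study procedures as separate possible causes.

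On injection-site reactions, Section 1.4 says of the overall Vigil experience: "These occur in essentially all Vigil treated patients". For the 31 Vigil patients in the Phase 2 ovarian study, the commonest related events were "injection site reactions of CTCAE Grade 1 or 2, which occurred in essentially all Vigil treated patients", with no related Grade 3 or 4 events.

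**The concern.** The primary objective is the tolerability and safety profile of the combination. A relatedness table is useful if it shows which events investigators ascribe to which agent. As written, the table pools the two, and one of them causes a mild local reaction in nearly every recipient. A subject with only a red injection site and a subject with immune-related toxicity both count as related in the overall row. That row is then largely fixed before any data arrive.

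A second loss concerns events that either agent could cause. Section 14.4 lists fever, chills or rigors, hypotension, hyperglycemia and local urticaria or rash for Vigil. The AESI list in Section 14.0 includes infusion-related reactions, influenza-like illness and diabetes mellitus, and the hold criteria in Section 6.2.2 include rash and hyperglycemia. On combination days the two agents are given 30 minutes apart, so onset time helps little. For these events the investigator's judgement by agent is the missing information. The Section 6.2.2 rule already requires that judgement for severe toxicity, but neither Section 14.1 nor Section 16.1 carries it into the record or the tables.

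**Working it through.** There is no planned figure to reproduce. Section 16.3 says the sample size has no statistical basis, and no related-AE rate is stated. The check is how far the overall related row can move with the atezolizumab rate.

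**Inputs**
- N = 20 to 25 (Section 5.1).
- q, the proportion of subjects with a related injection-site reaction. Section 1.4 gives no exact figure. If it was 31 of 31 in the Phase 2 study, the exact 95% lower limit is 0.025^(1/31) = 88.8%. I use 90%, 95%, 99% and 100%.
- a, the proportion with any atezolizumab-related AE. The documents give no figure. Assumed range: 0% to 80%.

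**Pooled any-grade related row**, assuming independence: 1 − (1 − q)(1 − a).

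| q | a = 0% | a = 20% | a = 60% | a = 80% |
|---|---|---|---|---|
| 90% | 90% | 92% | 96% | 98% |
| 95% | 95% | 96% | 98% | 99% |
| 99% | 99.0% | 99.2% | 99.6% | 99.8% |
| 100% | 100% | 100% | 100% | 100% |

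Independence is not essential: the proportion with either event cannot fall below q or exceed 100%, whatever the dependence.

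**In subjects.** At q = 95%, raising a from 20% to 60% moves the row from 96% to 98%, and 25 × 0.02 = 0.5 subject. The expected number without an injection-site reaction is 20 × 0.05 = 1.0 or 25 × 0.05 = 1.25. The chance that every subject has one is 0.95^20 = 36% or 0.95^25 = 28%. At q = 99% these become 82% and 78%.

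**Split by agent.** With N = 25, the same two cases would appear in an atezolizumab column as 5/25 = 20% (exact 95% CI 6.8% to 40.7%) and 15/25 = 60% (38.7% to 78.9%). The intervals are wide, but the row now moves with the quantity of interest.

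**Grade 3 or higher row.** Vigil contributed 0 of 31 (exact 95% CI 0% to 11.2%). With a Vigil rate v of 0%, this row equals the atezolizumab rate. With v at 11.2%, atezolizumab rates of 0%, 10% and 20% give 11.2%, 20.1% and 29.0% by the same formula. It is not saturated.

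**The case against.** The best defence is that one sentence is being read apart from the rest of Section 16.1. The related summary follows the same structure as the main AE tables, and the once-per-subject rule works within each system organ class and preferred term. Injection-site reactions therefore fill the any-grade row and their own rows, not those for pneumonitis, colitis or hepatitis. Section 16.1 also includes AESIs, which Section 14.0 defines around atezolizumab and its immune-related effects. All of that stands. A reader might infer that atezolizumab toxicity is hidden altogether; the documents do not support that.

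Other stronger readings also fail:
- That the related rate is 100% by construction. The figure is a projection. The lower Vigil dose of 1×10^6 cells is allowed, and an atezolizumab-first subject who stops before Cycle 3 never receives Vigil; either could lower it.
- That each event ascribed to the wrong agent costs 4 to 5 percentage points. That is only 1/25 to 1/20. Under a pooled rule, moving an event between agents changes the related rate by zero.
- That attribution by agent would show whether Vigil adds immune toxicity. That needs a comparison with atezolizumab alone, which investigator judgement does not supply.

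Two further points are fair. Relatedness to the regimen matches the primary objective, so the pooled figure should stay as one column. And the CRF, which is not in the documents, may already collect causality by agent, leaving only table layout at issue. Neither makes the pooled row informative, or attributes the overlapping events in the tables as planned.

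**Conclusion.** The point holds as a minor, inexpensive improvement to the safety analysis. As written, Section 16.1 gives one pooled relatedness summary for two agents, and its overall any-grade row is expected at about 90-100% whatever the atezolizumab-related rate. This assumes that reactions occur about as often as Section 1.4 reports, that investigators call them related, and that nearly all subjects receive Vigil. The atezolizumab range of 0% to 80% is assumed.

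The loss is confined to the any-grade row, the injection-site rows, and events either agent could cause. The Grade 3 or higher and preferred-term rows and the AESI evaluation still show typical immune-related events, though without attribution by agent. The documents attach no threshold or decision to the related-AE rate, so no trial conclusion turns on it. Sample size is unaffected.

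**What to change.** - **Section 14.1:** require relatedness to Vigil and to atezolizumab to be recorded separately for each event, if the CRF does not already do so.
- **Section 16.1:** tabulate related AEs for Vigil, for atezolizumab and for either, by worst grade. Show the overall related rate with and without injection-site reactions.
- **For whether Vigil adds immune toxicity:** also tabulate AEs by treatment period, Part 2 single-agent cycles against combination cycles. This addresses the question more directly, but only descriptively: the lead-in is two 21-day cycles (42 days), and Part 2 has about 17 to 22 subjects (20 to 25 less the 3 in the run-in) split between two sequences.

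The cost is at most one added CRF field and extra table columns. Treatment and sample size do not change. It should be done while data are being collected, because attribution reconstructed afterwards is less reliable.

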16.2 Efficacy Analysis

For each cohort, the ORR will be estimated, along with its two-sided exact binomial 95% confidence interval. The definitions of the response-related endpoints and corresponding time-to-event endpoints will be based on the programmatically-derived response from the investigator's recorded measurements and assessments for target, non-target, and new lesions according to RECIST 1.1. The distributions of PFS and OS will be estimated within each cohort using the Kaplan-Meier method.

16.3 Sample Size Justification

The sample size for this study is not based on statistical considerations. The results of this trial will be used to help design future studies.

17.0 STUDY RECORDS

17.1 Documentation

A log of all subjects evaluated for this protocol must be maintained at each site. Subjects excluded from admission will be provided with a clear explanation of the specific reasons why they have been excluded from the study. Subjects who have tumor tissue procured will be assigned a subject identification number.

For each subject treated with the study drug(s), the Research Coordinator is required to prepare and maintain case histories that include all observations and other data pertinent to the

investigation. This will include all source documents needed to verify the accuracy of all observations and other data contained in the eCRFs on each study subject.

The Investigator or his/her designee is required to retain the records related to the trial for a period of 2 years following the date a marketing application is approved for the indication being investigated. If no application is to be filed or if the application is not approved for such indication, the records must be retained until 2 years after the investigation is discontinued and the regulatory agencies are notified.

The Investigator shall retain study drug disposition records and source documents for the maximum period required by the country and institution in which the study will be conducted, or for the period specified by Gradalis, whichever is longer. The Investigator must contact Gradalis, Inc. prior to destroying any records associated with the study.

If the Investigator withdraws from the study (e.g., relocation, retirement), the records shall be transferred to a mutually agreed upon designee (e.g., another investigator, IRB). Notice of such transfer will be given in writing to Gradalis, Inc.

17.2 Case Report Form Procedures

Data for this study will be captured in the CRFs. The investigator or his/her designee is responsible for recording all data relating to the trial on the eCRFs in accordance with the site's contract with Gradalis. The investigator must verify that all data entries on the CRFs are accurate and correct.

APPENDIX A: PERFORMANCE STATUS SCALE

ECOG Performance Status Scale					
Grade	Description				
0	Normal activity. Fully active, able to carry on all pre-disease performance without restriction.				
1	Symptoms, but ambulatory. Restricted in physically strenuous activity, but ambulatory and able to carry out work of light or sedentary nature—(e.g., light housework or office work).				
2	In bed <50% of the time. Ambulatory and capable of all self care, but unable to carry out any work activities; up and about > 50% of waking hours.				
3	In bed >50% of the time. Capable only of limited self-care, confined to bed or chair >50% of waking hours.				
4	100% bedridden. Completely disabled; cannot carry out any self care; totally confined to bed chair.				
5	Dead				

APPENDIX B: SCHEDULE OF ASSESSMENTS

1 cycle = 3 weeks	Pre-Study ¹	Screening	Cycle 1	Cycle 2	Cycles 3, 6, 9, 12	Cycles 4, 5, 7, 8, 10, 11	EOT (30 days) ²	Response Follow-Up (quarterly) ³	Survival (3 years) ⁴
Visit Window		-2 weeks			±5 days			+/- 7 days	±4 weeks
Informed Consent	Х	within 4 weeks							
Medical History	Х	X							
Physical Exam	Х	X					Х		
Symptom-Directed Physical Exam ⁵			Х	Х	Х	Х	Х		
Performance Status (ECOG)		X	Х	X	Х	Х	Х		
Vital Signs (including weight) ⁶	Х	X	Х	X	Х	Х	Х		
Toxicity (adverse events)			Х	X	Х	Х	Х		
Concomitant Medications		x	х	x	Х	Х	Х	X ⁷	X ⁸
Radiological Tumor Assessment ⁹		within 4 weeks			X ¹⁰		X ¹¹	х	
Triplicate Electrocardiogram (ECG)		X			Х		Х		
CBC with differential	Х	X	Х	X	Х	Х	Х		
Serum Chemistry ¹²	Х	X	Х	X	Х	Х	Х		

CL-PTL-126 Page 50 of 60

Confidential and proprietary information of Gradalis, Inc.

Version: 04 Effective: 26-SEP-2018

It is the user's responsibility to verify adequate training before executing a document. Do not make unauthorized copies

¹ Pre-Study assessments including medical history, physical exam, CBC and Serum Chemistry may be obtained from medical records from standard preoperative hematology and chemistry panels.

² End of Treatment visit will occur 30 days (+ 5 days) after the last treatment or prior to commencement of subsequent treatment.

³ Subjects that discontinue study treatment before disease progression will have radiological assessment of disease quarterly until disease progression.

⁴ Assessment performed annually after disease progression.

⁵ Symptom-Directed Physical Exam performed by a medical provider.

⁶ Vital signs (including weight) must be obtained predose. Vital signs (heart rate, respiratory rate, blood pressure, temperature, and O₂ saturation) should also be obtained within 60 minutes prior to each atezolizumab infusion.

⁷ Collect any post study therapies taken after participation in the study.

⁸ Collect any post study therapies taken after participation in the study.

⁹ Radiological Tumor Assessment to include chest, abdomen, and pelvis. Assessment will be done per RECIST criteria for measurable disease.

¹⁰ Radiological Tumor Assessment will be performed at baseline and every third cycle thereafter.

¹¹ Radiological Tumor Assessment performed at End of TX if not done within the previous 45 days.

¹² Serum Chemistry to include creatinine, glucose, total protein, blood urea nitrogen, total carbon dioxide, albumin, total bilirubin, alkaline phosphatase, and aspartate transaminase and/or alanine transaminase and electrolytes (total calcium, chloride, potassium, sodium).

1 cycle = 3 weeks	Pre-Study ¹	Screening	Cycle 1	Cycle 2	Cycles 3, 6, 9, 12	Cycles 4, 5, 7, 8, 10, 11	EOT (30 days) ²	Response Follow-Up (quarterly) ³	Survival (3 years) ⁴
Visit Window		-2 weeks			±5 days			+/- 7 days	±4 weeks
CA-125 ¹³	Х	Х	Х	Х	Х	Х	Х	Х	Х
TSH ¹⁴		Х			Х				
Pregnancy Test (if applicable)		Х							
Immune Function Analysis ¹⁵	≤ 1 week of tumor procurement	x			х		х	х	
Tissue Procurement	Х								
Vigil Administration ¹⁶			Part 1: Both Part 2: Vigil or Atezolizumab		Х	Х			
Atezolizumab Administration ¹⁷					Х	Х			
Site Injection Assessment ¹⁸			х	X	Х	Х			
Tumor Biopsy					X ¹⁹				
Phone Contact	Х								Х

Version: 04 Effective: 26-SEP-2018

¹³ Obtain results from medical records when available.

¹⁴ TSH will be collected at screening and every third cycle thereafter.

¹⁵ Immune Function Analysis sample will be collected at baseline, prior to study agent administration at Cycle 3 and every 3 cycles thereafter.

¹⁶ Vigil Administration every 3 weeks on Day 1 as long as sufficient material is available and patient is deemed appropriate to continue. When combined, Vigil should be administered first, followed 30 minutes (+/- 5 min) later by atezolizumab.

¹⁷ Atezolizumab is to be administered at a dose of 1200 mg as an intravenous infusion on Day 1 every 3 weeks. The initial dose is to be administered over one hour and if well tolerated, subsequent infusions may be administered over 30 minutes.

¹⁸ Assessment of injection site will occur during the Vigil post-dose observation period and through 24 hours after Vigil dosing through patient contact.

¹⁹ Tumor biopsy for correlative studies including scoring of tumor infiltrating lymphocyte (TIL) and PD-1 / PD-L1 expression analysis will be obtained at tissue procurement, prior to Cycle 3 combination dosing (for individuals in Part 2) and at any time after the end of Cycle 3.

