- 7. History of or current evidence of any condition (including medical, psychiatric or substance abuse disorder), therapy, or laboratory abnormality that might confound the results of the study, interfere with the patient's participation for the full duration of the study, or is not in the best interest of the patient to participate, in the opinion of the treating Investigator.
- 8. Receipt of the last dose of anti-cancer therapy (chemotherapy, immunotherapy, endocrine therapy, targeted therapy, biologic therapy, tumor embolization, monoclonal antibodies, other investigational agent) less than 21 days prior to tissue procurement.

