5.5 Study Enrollment Exclusion Criteria

In addition to the procurement exclusion, subjects (both with Vigil manufactured and undergoing procurement) will NOT be eligible for study registration and enrollment if meeting any of the following criteria:

- 1. Participation in another clinical study with an investigational product within the last 3 weeks prior to study start.
- 2. Receipt of steroid therapy within the 2 weeks of the first dose of study therapy.
- Live vaccine used for the prevention of infectious disease administered < 30 days prior to the start of study therapy. NOTE: Subjects, if enrolled, should not receive live vaccine during the study and for 5 months after the last dose of atezolizumab.
- 4. Post-surgery complication that in the opinion of the treating investigator would interfere with the subject's study participation or make it not in the best interest of the subject to participate.
- 5. Mean QT interval corrected for heart rate (QTc) ≥470 ms calculated from 3 electrocardiograms (ECGs) using Fridericia's Correction.
- 6. Female subjects who are pregnant, breast-feeding or of reproductive potential who are not employing an effective method of birth control defined in the protocol. Effective contraception is required for women receiving atezolizumab for 5 months after the last dose.

- 7. Any condition that, in the opinion of the investigator, would interfere with evaluation of study treatment or interpretation of patient safety or study results.
- 8. Receipt of the last dose of anti-cancer therapy (chemotherapy, immunotherapy, endocrine therapy, targeted therapy, biologic therapy, tumor embolization, monoclonal antibodies, other investigational agent) less than 21 days prior to the first dose of study drug or less than 6 weeks for nitrosourea or mitomycin C.
- 9. Receipt of any anti-cancer therapy between tissue procurement on CL-PTL-126 and first dose of study drug.

Patients should continue the combination of Vigil with atezolizumab until disease progression is documented, or toxicity supervenes. Depending on the number of doses of Vigil manufactured, it is expected that 4 to12 doses of Vigil will be administered. Once Vigil doses are exhausted, subjects whose disease is stable or responding, may continue to receive single agent atezolizumab until disease progression.

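### The immune-function baseline can be drawn up to 14 days before dosing, but the steroid and anti-cancer washouts are counted to the first dose, so it can fall inside the washout

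*Combined protocol and SAP*

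**What the plan says.** **Sampling.** Appendix B, footnote 15: "Immune Function Analysis sample will be collected at baseline, prior to study agent administration at Cycle 3 and every 3 cycles thereafter". The immune-function row has two pre-treatment entries: one in the Pre-Study column, "≤ 1 week of tumor procurement", and one at Screening, whose visit window is -2 weeks. The Cycle 1 and Cycle 2 cells are empty. The footnote does not say which pre-treatment sample is the baseline.

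**Washouts.** Section 5.5 item 2 excludes "Receipt of steroid therapy within the 2 weeks of the first dose of study therapy". Item 8 excludes anti-cancer therapy "less than 21 days prior to the first dose of study drug or less than 6 weeks for nitrosourea or mitomycin C". Both clocks stop at the first dose. Item 9 also excludes "Receipt of any anti-cancer therapy between tissue procurement on CL-PTL-126 and first dose of study drug", and Section 5.3 item 8 excludes anti-cancer therapy "less than 21 days prior to tissue procurement".

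**Use.** The first secondary objective in Section 3.2 is the immune response rate and how long conversion lasts, for each agent and for the combination. The protocol gives no conversion rule of its own, and Section 16.2 has no immune-response analysis. The only positivity rule in the documents is the earlier Phase 2 trial's, in Section 1.4: more than 10 spots per million "peripheral blood mononuclear cells (PBMC) and twice baseline response".

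**The concern.** A washout protects a baseline only if it is complete when the baseline is drawn. Here the sample may come up to 14 days before the point to which the washouts are counted. If recent steroid or chemotherapy lowers the ELISPOT count, the subject starts from an artificially low value, and a later return to the usual level can look like an immune response.

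The absolute rates are at stake: the proportion responding to Vigil alone, to atezolizumab alone and to the combination. Section 16.3 says the results will help design future studies, so those rates are likely to be carried forward.

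**Working it through.** The plan gives no figure for this point, so there is none to reproduce.

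**1. Shortest permitted gap.** Gap from last drug to sample = washout to first dose (W) minus days from sample to first dose (d, from 0 to 14).

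| Washout W (Section 5.5) | Day -14 | Day -7 | Day -1 | Cycle 1 Day 1, pre-dose |
|---|---|---|---|---|
| Steroid, 14 days | 14 - 14 = 0 | 7 | 13 | 14 |
| Anti-cancer, 21 days | 21 - 14 = 7 | 14 | 20 | 21 |
| Nitrosourea or mitomycin C, 42 days | 42 - 14 = 28 | 35 | 41 | 42 |

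**2. Who can be at the short end.**
- *Steroid.* Formally any subject. Section 5.3 item 1, carried into enrollment by Section 5.5, bars conditions needing chronic systemic immunosuppression, apart from short-term physiologic replacement. The 0-day case is therefore mainly a short course or a replacement dose.
- *Anti-cancer, tissue procured on CL-PTL-126.* At least 21 days before procurement, then none until first dose. The Screening sample is at least 21 days clear, so the 7-day case cannot occur.
- *Anti-cancer, tissue not procured on CL-PTL-126* (for example, Vigil made from CL-PTL-119 tissue). Item 9 does not apply, chemotherapy may follow procurement, and 7 days is permitted.

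**3. When recovery would count.** Take the earlier trial's rule as an assumption. Let b be the true baseline and m the measured one, with m below b. The twice-baseline condition binds only if 2b exceeds 10, that is b above 5; below that, the 10-spot floor decides and a low m changes nothing. For recovery alone to turn a negative subject positive, m must be 10 or less, b above 10, and b at least 2m.

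**4. How often that might happen.** Let q be the share positive without Vigil in Section 1.4. The expected number of false conversions in N = 20 to 25, if every such subject were suppressed at baseline (an extreme assumption), is N × q.

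| Source | q (exact 95% CI) | N × q |
|---|---|---|
| Phase 2 Vigil patients at baseline, 1/31 | 3.2% (0.1 to 16.7) | 0.6 to 0.8 |
| First-in-human study at baseline, 1/18 | 5.6% (0.1 to 27.3) | 1.1 to 1.4 |
| Controls at relapse, at most 1/8 | 12.5% (0.3 to 52.7) | 2.5 to 3.1 |

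The first two rates were themselves measured at baseline and may be suppressed, so they are not firm upper bounds.

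**5. Effect on a rate.** Observed rate = p + (1 - p) × s × q, where p is the true conversion rate and s the share of subjects suppressed (both assumed).
- p = 0.5, s = 0.25, q = 1/31: 0.5 + 0.5 × 0.25 × 0.032 = 0.504.
- p = 0.5, s = 1, q = 1/8: 0.5 + 0.5 × 0.125 = 0.5625.
- p = 0.3, s = 1, q = 1/8: 0.3 + 0.7 × 0.125 = 0.3875.
- p = 0.9, s = 1, q = 1/8: 0.9 + 0.1 × 0.125 = 0.9125.

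**6. Weight of one subject.** 20 to 25 enrolled less 3 in Part 1 leaves 17 to 22. Split about equally (assumed), that is 8 to 11 per lead-in arm. One false conversion moves an arm by 1/11 = 9.1 to 1/8 = 12.5 percentage points. This is the step size of the estimate, not an estimated bias.

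**The case against.** **Other criteria narrow the gap.** Section 5.4 item 7 requires recovery to Grade 1 or better from prior-therapy adverse events for registration. Item 6 sets neutrophil, platelet and hemoglobin limits. These make heavy suppression less likely, but none sets an interval before the sample and none limits lymphocytes. Item 13 ties recovery to starting treatment, not to the draw. Section 11 restricts therapy from screening onward and sets no gap before it. The gap is narrowed, not closed.

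**The documents' own data point to a small effect.** In Section 1.4, 7 of the 8 control patients who crossed over were ELISPOT-negative at relapse, before any Vigil. Time since chemotherapy alone rarely produced positivity there. This stands, with the caution that eight patients is few.

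**The mechanism relies on another trial's rule.** True. But any rule that compares with baseline shares the problem, and an objective on conversion and its duration needs some such comparison.

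**Screening may not be the baseline.** The documents do not settle this. Section 1.4 equates baseline with screening in the earlier trial, and footnote 14 uses screening followed by every third cycle for TSH, so Screening is the natural reading. The procurement sample is a poor substitute when chemotherapy follows the harvest.

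**It is a secondary endpoint in a safety study.** True, and it limits the weight of the point. The correction is still cheap.

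**Conclusion.** The point holds in a limited form. The baseline sample can precede the end of the washout by up to 14 days, leaving 0 days off steroids and, for subjects not procured on CL-PTL-126, 7 days off anti-cancer therapy. If counts are then depressed, the absolute immune response rates can be inflated. The documents do not give the depth or duration of suppression, so the size is unknown. It is probably small: on the assumptions above, an assumed 50% true rate reads as 50.4% to 56.25%.

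A reader might infer more than the documents support:
- *Every reported rate is biased upward.* Not shown. Section 11 permits short low-dose systemic and inhaled steroids on study, which could lower the Cycle 3 count and push the other way.
- *The Cycle 3 sample has a guaranteed long drug-free interval.* It does not, given those steroids and the ±5-day visit window.
- *The 7-day case is typical.* Incomplete response after standard chemotherapy is a named entry group, but the documents give neither the mix of groups nor the timing of screening.
- *The randomized comparison is invalid.* Both lead-in arms share the baseline procedure, so the difference is less exposed than the rates. It is not fully protected: an arm near 100% has little room to rise (1.25 points at p = 0.9 against 8.75 at p = 0.3 in the extreme case).

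**What to change.** In Appendix B, move the Screening immune-function draw to Cycle 1 Day 1, before any study agent. State in footnote 15 that this sample is the baseline for conversion and duration, and that the procurement sample is descriptive only. The baseline is then at least 14 days after steroids and 21 days after anti-cancer therapy (42 for nitrosourea or mitomycin C), and it is pre-dose like the Cycle 3 sample. The eligibility washouts stay as they are.

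The cost is one table edit and one footnote in an amendment. CBC and chemistry are already drawn at Cycle 1, so no extra visit is needed, and no eligibility rule uses the assay. The downside is small: the baseline result is not available before treatment starts, and a missed pre-dose draw cannot be replaced.

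For subjects already sampled at Screening, record the days since last steroid and anti-cancer therapy, and repeat the analysis without those inside 14 or 21 days. The missing conversion rule is a separate gap that this change does not fill; it should be stated too.
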